4. OBJECTIVES

4.1. Primary Objective

To compare the efficacy of the ACT artemether-lumefantrine versus a multivitamin preparation as defined by the 28-day PCR parasite positivity rate and incidence of confirmed clinical malaria of any species.

4.2. Secondary Objectives

1. To compare the efficacy of the ACT artemether-lumefantrine versus a multivitamin preparation as defined by the 28-day, 56-day and 84-day PCR parasite positivity rate and incidence of confirmed clinical malaria for each species.

2. To quantify the impact of the ACT artemether-lumefantrine as prophylaxis for forest goers on overall malaria transmission using mathematical modelling.
3. To assess the impact of artemether-lumefantrine prophylaxis on the spread of genetic markers of artemisinin (such as *Kelch13* mutations) and partner drug resistance.
4. To obtain data on the place of residence, work, recent travel history and risk behaviours of forest goers in order to improve the understanding of high risk groups, locations of malaria transmission and possible routes spread of malaria and artemisinin resistance.
5. To explore the duration, location and purpose of individual forest visits.
6. To obtain detailed data and GPS mapping on a subset of participants and their peers relating to the behaviours and risk factors associated with malaria infection in order to improve understanding of local malaria transmission among forest goers.
7. To determine the prevalence of asymptomatic *Plasmodium* infections in high risk populations at varying seasonal time points.
8. To determine the prevalence of other infectious diseases that affect the study population

5. TRIAL DESIGN

5.1 Study sites

The study will take place at up to 50 villages in selected malaria endemic districts in Stung Treng and Pursat Provinces, Cambodia. As the malaria situation in these areas is dynamic, the villages will be identified prior to the start of the trial from analysis of up to date malaria incidence from passive surveillance collected by the Cambodia National Center for Parasitology Entomology and Malaria Control. If there are found to be insufficient villages with malaria cases in Stung Treng Province at the time of trial commencement, we will include additional sites in Pursat Province. MORU has existing study sites and teams in both provinces which will support the running of this trial. The rationale for choosing these areas include high forest cover and ongoing malaria transmission among forest goers.

5.2 Summary of trial design

An open-label randomised trial among forest goers comparing the ACT AL with a multivitamin with no antimalarial activity to evaluate the efficacy of prophylaxis, and to better understand high risk groups and locations of malaria transmission.

5.3 Study duration

The recruitment phase of the study is expected to last 12 months following the intended start of recruitment in September 2019. Training and community sensitization will precede study execution for 3 months. Data management and analysis, sample analysis (PCR, parasite genetics), mathematical modelling and report writing are expected to take about 5 months. Therefore, the total time to complete the study will be about 20 months.

5.4 Primary and secondary endpoints

5.4.1. Co-primary Endpoints

1. 28-day PCR positivity rate of *Plasmodium* infections of any species.
2. Proportion of participants with confirmed clinical malaria of any species reported between day 0 and day 28

5.4.2. Secondary Endpoints

1. 28-day, 56-day and 84-day PCR *Plasmodium* positivity rate for each *Plasmodium* species

2. Proportion of participants with confirmed malaria reported between day 0 and day 28 for each species
3. Description of epidemiological situation of malaria in the study areas from passive surveillance data.
4. Prevalence of *Kelch13* mutations and other genetic markers of antimalarial drug resistance of known functional significance.
5. Incidence of adverse events and serious adverse events by study arms during the course of prophylaxis.
6. Data on the place of residence, work, recent travel history and mobile phone use.
7. Detailed data and GPS mapping on a subset of participants and their peers relating to the behaviours and risk factors associated with malaria infection.
8. Overall prevalence of Plasmodium at baseline, stratified by season and risk factors.
9. Day 0, 28, 56 and 84 capillary blood levels of lumefantrine.
10. Prevalence of serological diagnostic markers of other infectious diseases.

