6.6. Follow-up

Participants will be asked to return for a follow-up assessment any time from 28 to 35 days after commencing prophylaxis. This will be regardless of the duration of their visit to the forest or the number of times they visited it in that period. At this assessment, they will be interviewed about how long they spent in the forest, where they went, why, who they travelled with and about risk factors for infection. Brief physical examinations, vital sign and symptom questionnaire will be performed. They will also be asked to report any diagnostic tests and/or treatment for malaria during the preceding 28-35 days.

Blood sampling at follow-up

At each follow-up visit, the following blood will be taken:

All individuals:

- Parasite PCR (Up to 1 ml).

- Dried blood spot for lumefantrine level (0.2 ml)

In those with confirmed clinical malaria at any time point between enrolment and follow-up:

- Dry blood blots (0.4 ml, 3 spots) collected on filter papers for:
 - o Parasite DNA genotyping for genetic markers of antimalarial resistance.
 - o Parasite whole genome sequencing and barcoding to identify geographical origin of parasites and compare genotypes to identify persistent infections.

In individuals who are planning to return again to the forest within the following 28 days after the follow up visit, they will be asked to continue their weekly prophylaxis according to the original treatment allocation on enrolment. They will then be asked to return for a second follow-up visit a further 28 to 35 days later when the above procedure will be repeated. This will be repeated one more time. If the person cannot be followed up within the scheduled period, e.g. because they do not return from the forest in time, then they will be followed up at the first opportunity and this will be recorded in the CRF.

Thus individuals may take prophylaxis continuously for a maximum of 3 periods of 28-35 days in the forest plus 4 weeks after returning totaling 112 days. The choice of study medication for each individual will follow the initial assignment on enrolment throughout the follow-up period.

In those who do not declare an intention to return to the forest within 28 days at any follow-up visit, no further follow-up visits will be offered at that time but they will be asked to complete 4 weeks of prophylaxis following their last day in the forest as post-exposure prophylaxis.

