6.8.2 Parasite genetic analysis

Blood samples (dried blood spots) for parasite genetic analysis will be obtained and stored from all subjects recruited with subject's consent. In individuals in whom parasites are found by PCR, samples will be processed for parasite genetic analysis. Genetic samples (in the form of dried blood spots or extracted DNA) will be stored (for a maximum of 10 years) at the Molecular Tropical Medicine Laboratory, Bangkok, Thailand. In those with confirmed clinical malaria, parasite genotyping will be performed at the Wellcome Trust Sanger Institute in Hinxton, UK or other suitable laboratory using a set of informative single nucleotide polymorphisms selected from whole genome sequencing. The subject will be asked for consent for this transfer during the initial informed consent process. A material transfer agreement will be in place if required before any samples are shipped. The results of the parasite genotyping will not be reported back to the subjects. This analysis will only be done for those with confirmed clinical malaria as it is anticipated that there will be insufficient genetic material in samples taken from those with asymptomatic infection due to the low parasite burden in these individuals.

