# 4.4.3 Assessing the impact of artemether-lumefantrine prophylaxis on the spread of genetic markers of artemisinin (such as Kelch13 mutations) and partner drug resistance.

The prevalence of *Kelch13* mutations and other genetic markers of antimalarial drug resistance of known functional significance will be analysed and presented in table 4 below.

Table 4 Day 28 -PCR positivity by resistance markers e.g. Pfkelch	h13 status
---	------------

	Detection of relevant	Detection of relevant Pfkelch13 mutation		
	Yes	No (wild type)	Risk Difference	p-value
	(N=XXX)	(N=XXX)	(95% CI)	
Artemether-	XX.X (X.X)	XX.X (X.X)	XX.X (X.X)	X.XXX
Lumefantrine				
Multivitamin	XX.X (X.X)	XX.X (X.X)	XX.X (X.X)	X.XXX

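### A marker share among infected, genotyped people cannot on its own show whether AL spreads resistance; add a comparison per randomised episode

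*Protocol*

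**What the plan says.** **The question.** Objective 3 (Protocol 4.2) is causal: "To assess the impact of artemether-lumefantrine prophylaxis on the spread of genetic markers of artemisinin" and partner-drug resistance.

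**The measure.** Endpoint 4 (Protocol 5.4.2) is the prevalence of Kelch13 mutations and "other genetic markers of antimalarial drug resistance of known functional significance". It gives no denominator, time point or contrast between arms.

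**The analysis.** SAP 4.4.3 repeats this measure, Kelch13 included, and says that "other genetic markers of antimalarial drug resistance of known functional significance will be analysed and presented in table 4 below". The shell is titled "Table 4 Day 28 -PCR positivity by resistance markers". Its rows are the two arms. Its columns are mutation detected, wild type, a risk difference and a p-value. Episodes without infection have no place in it.

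**Who is genotyped.** Protocol 6.6 takes the genetic blood spots at follow-up "In those with confirmed clinical malaria at any time point between enrolment and follow-up". Protocol 6.8.2 makes two statements that do not agree: "In individuals in whom parasites are found by PCR, samples will be processed for parasite genetic analysis", and later "This analysis will only be done for those with confirmed clinical malaria", on the ground that asymptomatic infections will yield too little genetic material.

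**The concern.** A marker can be read only from a parasite, so a marker share describes people who became infected (or fell ill with malaria) and were then genotyped. Infection and clinical malaria are the co-primary endpoints, so the plan itself expects AL to change who is in that group. A comparison of shares between arms is therefore conditional on something that happens after randomisation, and it loses the protection that randomisation gives.

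Spread depends on how many resistant infections arise per person given AL rather than multivitamin. If AL removes wild-type infections more readily than mutant ones, the mutant share rises on AL even when AL also prevents mutant infections. The two measures can then point in opposite directions, on a question that bears on whether AL prophylaxis should be adopted. Neither document plans to report marker-carrying infections per randomised episode.

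**Working it through.** **Inputs from Protocol 9.1 (SAP 2.5 gives the same figures).** *P. falciparum* positivity 5% on multivitamin and 3% on AL; 80% power; 5% significance; 1,605 episodes per arm before and 2,200 after the allowance for repeat episodes and loss.

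**The plan's own figure.** With p1 = 0.05, p2 = 0.03, mean p = 0.04, z = 1.960 and 0.842:

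- n = [1.960 × √(2 × 0.04 × 0.96) + 0.842 × √(0.05 × 0.95 + 0.03 × 0.97)]² / 0.02² = 1,505.8
- with continuity correction, (n/4) × [1 + √(1 + 4/(n × 0.02))]² = 1,604.2, rounded up to **1,605**

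The stated figure is reproduced (two-sided, continuity-corrected).

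**General rule.** The overall risk ratio is 0.03/0.05 = 0.6. Let m be the mutant share on multivitamin, and RRm and RRw the risk ratios on AL for mutant and wild-type infection. Then

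- 0.6 = m × RRm + (1 − m) × RRw
- mutant share on AL = m × RRm / 0.6

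The share rises when RRm exceeds 0.6. The number of mutant infections falls when RRm is below 1. Both hold for any mutant-specific efficacy above 0% and below 40%. At exactly 40% against both genotypes the share does not move.

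**Worked case** (assumed: m = 50%, RRm = 0.8, hence RRw = 0.4), at 2,200 per arm, so 110 infections on multivitamin and 66 on AL:

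- mutant infections 55 v 55 × 0.8 = 44; wild type 55 v 55 × 0.4 = 22
- share among infected: 55/110 = 50.0% v 44/66 = 66.7%, Fisher p = 0.041
- per randomised episode: 55/2,200 = 2.5% v 44/2,200 = 2.0%
- difference −0.5 points; SE = √(0.02 × 0.98/2,200 + 0.025 × 0.975/2,200) = 0.45 points; 95% CI −1.4 to +0.4, treating episodes as independent

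**Range over assumed inputs (2,200 per arm, overall risk ratio held at 0.6).**

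| Share on multivitamin | Efficacy v mutant | Share on AL | Mutant infections per episode, AL v multivitamin |
|---|---|---|---|
| 30% | 10% / 20% / 30% | 45% / 40% / 35% | 1.35% / 1.20% / 1.05% v 1.50% |
| 50% | 10% / 20% / 30% | 75.0% / 66.7% / 58.3% | 2.25% / 2.00% / 1.75% v 2.50% |
| 70% | 20% / 30% | 93.3% / 81.7% | 2.80% / 2.45% v 3.50% |
| any of these | 40% on both genotypes | unchanged | 40% fewer |

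At a 70% share, 10% efficacy cannot occur with an overall ratio of 0.6, because 0.7 × 0.9 = 0.63 already exceeds it.

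**How far the p-value depends on the counts** (same worked case):

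- all infections genotyped, 2,200 per arm: 44/66 v 55/110, p = 0.04
- all genotyped, 1,605 per arm: 32/48 v 40/80, p = 0.07
- half genotyped: 22/33 v 28/55, p = 0.18 (0.13 if the odd 55 is rounded to 27 mutant)
- a quarter genotyped: 11/17 v 14/28, p = 0.37

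With a 30% share on multivitamin and all genotyped, 26/66 v 33/110 gives p = 0.25.

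**The case against.** **The plan does not specify the comparison criticised.** The infected-only denominator is an inference from Protocol 6.6, 6.8.2 and the two genotype columns. In the shell, the risk difference and p-value sit in each arm's row beside those columns, so as extracted it gives no clear AL v multivitamin contrast. This stands. A reader might infer that the trial, as planned, would test the shares and declare that AL promotes resistance. The documents do not say that; the Fisher test above is an illustration.

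**The driver is assumed.** The documents give no mutant share and no genotype-specific efficacy, and Protocol 3.1 and 3.2 describe AL efficacy as still high. This stands, so the point is only that the two measures can diverge.

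**The counts are generous.** The case of 110 v 66 genotypes every PCR infection with no loss, while Protocol 6.8.2 confines the analysis to clinical malaria. This stands; real counts will be smaller.

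**A higher share is informative.** It is a genuine sign of selection. If AL had no effect on mutants, a rise from 50% to 83% (0.5 × 1.0/0.6) would be an important finding. This stands and is why the share should be kept. Selection is still a different quantity from the number of resistant infections per person.

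**Part of the answer lies elsewhere.** SAP Table 3 reports *P. falciparum* outcomes by arm, which could be multiplied by a share by arm, and SAP 2.3 defers detail on some endpoints to specialised groups. The product would have no planned confidence interval, and it would apply the share from genotyped cases to infections that were never genotyped. This answers the point only in part.

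**Conclusion.** The point holds in a limited form. As far as the sampling rules and the table shell show, endpoint 4 summarises markers among infected, genotyped people, and that share alone cannot answer objective 3. At the planned rates, a mutant-specific efficacy above 0% and below 40% would give a higher mutant share on AL together with fewer mutant infections. This rests on AL protecting less against mutant than wild-type parasites.

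Two stronger readings are tempting and unsupported. One is that the endpoint will point the wrong way: with equal efficacy it does not, and the documents give no figure that would decide. The other is that a misleading significant result is likely: p = 0.04 is the best case, and smaller genotyped counts move it to between 0.07 and 0.37. This is one secondary endpoint, and the change is worth making because the question matters and the cost is low.

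**What to change.** - **Protocol 5.4.2 endpoint 4 and SAP 4.4.3:** state the denominator, time window and arm contrast. Add an AL v multivitamin comparison of the risk of a marker-carrying *P. falciparum* infection and the risk of a wild-type *P. falciparum* infection, with all randomised episodes as denominator. Give a risk difference or ratio with 95% CI, using the participant-level robust standard error already planned in SAP 4.3.
- **Same table:** add an infected-but-not-genotyped row by arm.
- **Keep** the mutant share among genotyped infections by arm as a measure of selection, labelled as conditional on infection.
- **Protocol 6.8.2:** reconcile the two statements on who is genotyped. If only clinical cases are, define the outcome as genotyped clinical *P. falciparum* malaria carrying the marker, per randomised episode.

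**Cost.** Wording and one table shell; no new samples or data. The per-episode estimate will be imprecise: in the worked case the interval of −1.4 to +0.4 points does not settle the direction. If many infections are not genotyped, it is a lower bound on marker-carrying infections. If the proportion genotyped differs by arm, the difference between arms is distorted too, so the ungenotyped row must be read with it.

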5.5 Trial Participants

5.5.1 Overall Description of Trial Participants

Male and non-pregnant female participants aged between 16 years and 65 years planning to visit the forest within 72 hours are the target study population. All study participants must meet the applicable inclusion and exclusion criteria.

5.5.2 Inclusion criteria

- Male or female, adults aged between 16 and 65 years.
- Planning to travel to the forest within the next 72 hours and stay overnight.
- Written informed consent.
- Willingness and ability of the participants to comply with the study protocol for the duration of the study.

5.5.3 Exclusion criteria

- For females: known pregnancy or breast feeding
- Participants who have received artemisinin or a derivative or an artemisinin-containing combination therapy (ACT) within the previous 7 days.
- History of allergy or known contraindication to artemisinins, lumefantrine or multivitamins
- Documented or claimed history of cardiac conduction problems
- Severe vomiting or diarrhoea
- Signs/symptoms of clinical malaria (febrile or history of fever in the previous 24 hours) confirmed by RDT.

6. PROCEDURES

Study procedures will be performed according to the schedule of assessments (Appendix 1). This will require that participants are followed up every 28 days for up to 3 periods upon completion of a course of prophylaxis.

6.1. Informed Consent

Prior to the start of enrollment we will conduct community mobilisation and sensitisation activities in each village community where the trial will recruit participants. During the trial, the participant (or witness if illiterate) must personally sign and date the latest approved version of the informed consent form before any study specific procedures are performed. Written and verbal versions of the participant information and informed consent in the local language will be presented to the participants detailing no less than: the exact nature of the study; the implications and constraints of the protocol; the known side effects and any risks involved in taking part. It will be clearly stated that participation is voluntary and that the participant is free to withdraw from the study at any time for any reason without prejudice to future care, and with no obligation to give the reason for withdrawal.

The participant will be allowed as much time as possible to consider the information and take the opportunity to question the Investigator, or other independent parties to decide whether they will (or allow his/her charge to) participate in the study. Written informed consent will then be obtained by means of participant dated signature or thumb print (if unable to write) and dated signature of the person who presented and obtained the informed consent.

A copy of the signed informed consent document(s) will be given to the participants.

Children aged 16 - <18 years will be required to sign the latest approved version of the written informed assent form in addition to their parent or guardian signing a consent form.

6.2. Screening, Eligibility and Baseline Assessments

Participants who present at the participating sites will be screened to assess eligibility. Full consent will be obtained before any enrolment procedures are conducted. It will be made clear from the outset that refusal to participate will not jeopardise subsequent antimalarial treatment (if applicable). A screening log will be kept.

6.2.1. Demographics and Medical History

Basic demographic and epidemiological data (e.g. sex, age, weight, address, bed net use, malaria risk factors, travel history, prior malaria episodes, prior treatment and previous participation in this or previous studies), and a full medical history will be recorded by the study staff.

6.2.2. Physical Examination and Vital Signs

Brief physical examination and vital sign will be conducted by a qualified study team member. Weight and temperature. A symptom questionnaire will be performed.

6.2.3. Drug history

All prescribed or over-the-counter and traditional antimalarial medications used within the last 7 days will be recorded. Any drug allergies will be recorded.

6.2.4. Clinical malaria

Participants who are screened and are found to be febrile or have a current history of fever will not be enrolled (as per exclusion criteria) but will be tested for malaria and, if positive, given antimalarial treatment by the village malaria worker or local clinic. All this will be done in accordance with the current national malaria treatment guidelines in Cambodia. Individuals treated for malaria in this way will not be enrolled in the study as per the exclusion criteria.

6.3. Randomisation and blinding

Participants who fulfil all the inclusion criteria and have none of the exclusion criteria will be randomised 1:1 to one of the two treatment arms according to a randomisation schedule. Randomisation will be in blocks of size that will be determined by the trial statistician and the block

size will not be revealed to the investigating team. Allocation will be done by drawing the next sequential numbered opaque envelope (or other equally reliable randomisation administration procedure), which contains the study number and treatment allocation.

The participants will be assigned a study arm through a computer-generated randomisation schedule. Individual, sealed and sequentially numbered envelopes will be provided for each trial site with one envelope per participant, indicating the treatment allocation.

This is an open-label study so the blinding of investigators and participants is not applicable. However, the randomisation procedure allows for adequate drug allocation concealment before envelopes are opened. All laboratory investigations will be performed without knowledge of the treatment allocation.

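### Withholding the block size does not by itself assure allocation concealment in this open-label trial; the protocol should state that block sizes vary and define the site that holds an envelope series

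*Protocol*

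**What the plan says.** Everything on this point is in protocol section 6.3; the SAP does not describe the randomisation.

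- **Method.** Allocation is 1:1. "Randomisation will be in blocks of size that will be determined by the trial statistician". No size is given, and nothing says whether it is fixed or varies. The stated safeguard is secrecy: the "size will not be revealed to the investigating team".
- **Administration.** "Allocation will be done by drawing the next sequential numbered opaque envelope (or other equally reliable randomisation administration procedure"). Also: "Individual, sealed and sequentially numbered envelopes will be provided for each trial site with one envelope per participant, indicating the treatment allocation".
- **Blinding.** "This is an open-label study so the blinding of investigators and participants is not applicable". The laboratory is the exception: "All laboratory investigations will be performed without knowledge of the treatment allocation".
- **Claim.** The protocol states that "the randomisation procedure allows for adequate drug allocation concealment before envelopes are opened".

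Section 6.5 has study staff giving the drug, so staff learn the arm of each person they treat. Section 5.1 plans up to 50 villages in two provinces. It does not say whether the trial site that holds an envelope series is a village, a province or a team.

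**The concern.** An opaque sealed envelope hides what is inside it. It does not stop someone inferring the content from envelopes already opened. In balanced blocks, once one arm is used up, the rest of the block is determined. A person who knows the block size and has seen the block so far then knows the next allocation. In a blinded trial past allocations are hidden, so withholding the size adds real protection. Here past allocations are visible, and a fixed size can be read off them.

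The stake is selection at enrolment. Eligibility rests on a stated plan to enter the forest within 72 hours and stay overnight (section 5.5.2), so staff have some influence over who takes the next envelope and when. Re-enrolment with fresh randomisation, up to three enrolments per person (section 6.6), adds occasions to time an entry. Section 9.1 treats nights in the forest as the driver of infection, at 1 infection per 500 person-nights. Steering longer trips towards one arm would alter the risk in that arm, while the planned contrast is only 5% against 3%. Blinded PCR protects the reading of the outcome, not the choice of who is enrolled.

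**Working it through.** The plan gives no figure for block size or predictability, so there is none to reproduce.

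**Inputs.** From the protocol: 1:1 allocation in blocks (6.3), 4,400 episodes (9.1), up to 50 villages (5.1). Assumed: block sizes of 4 to 10; an observer who sees every past allocation in a series; a series of 4,400/50 = 88 envelopes, which would be the average if each village held its own series.

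**Step 1. Certain allocations once a fixed size is known.** In a block of 2m, the expected number of determined envelopes at the end is 2m/(m+1).

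**Step 2. Best guess.** Always guessing the arm with more places left gives an expected m + 2^(2m)/(2·C(2m,m)) − 1/2 correct per block. Simple randomisation would give 50%.

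| Block | Determined per block | Share certain | Correct guesses per block | Share correct |
|---|---|---|---|---|
| 4 | 4/3 = 1.33 | 33% | 2 + 16/12 − 0.5 = 2.83 | 71% |
| 6 | 6/4 = 1.50 | 25% | 3 + 64/40 − 0.5 = 4.10 | 68% |
| 8 | 8/5 = 1.60 | 20% | 4 + 256/140 − 0.5 = 5.33 | 67% |
| 10 | 10/6 = 1.67 | 17% | 5 + 1024/504 − 0.5 = 6.53 | 65% |

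Over exactly 88 envelopes, blocks of 4 and 8 fit evenly. Blocks of 6 leave 14 full blocks and 4 further envelopes. Only the fourth of those can be determined, when the first three share an arm: 2 × (3/6)(2/5)(1/4) = 0.1. The share is (14 × 1.5 + 0.1)/88 = 24%.

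**Step 3. Learning the size.** The simulated observer starts with equal weight on fixed sizes 2, 4, 6, 8, 10 and 12 and updates after each envelope (1,000 series per case). The median is over series that reached 95% weight on the true size.

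| Series length | True block | Reach 95% weight on true size | Median envelopes to reach it | Share predictable at ≥95% confidence, learning counted |
|---|---|---|---|---|
| 44 | 4 / 6 / 8 / 10 | 81 / 73 / 64 / 82% | 36 / 42 / 20 / 23 | 16 / 10 / 10 / 8% |
| 88 | 4 / 6 / 8 / 10 | 100 / 100 / 97 / 98% | 42 / 42 / 36 / 24 | 25 / 17 / 15 / 12% |
| 440 | 4 / 6 / 8 / 10 | 100% in each | 42 / 42 / 35 / 24 | 32 / 23 / 19 / 16% |

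A longer series is at least as easy to learn if the same people see it all.

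**Step 4. Randomly varying sizes.** Here the observer is allowed to know the set of sizes but not their order, over 88 envelopes.

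| Scheme | Certain | Best guess correct |
|---|---|---|
| Fixed 4 | 33% | 71% |
| Fixed 6 | 24% | 68% |
| Fixed 8 | 20% | 67% |
| Random 4/6 | about 5.5% | 69% |
| Random 4/6/8 | about 2.3% | 68% |

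For both mixes, counting predictions held with at least 95% confidence instead of certain ones gave the same shares. The gain is therefore in near-certain allocations. On best guessing, a 4/6/8 mix is slightly worse than a fixed block of 8.

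**Not computed.** The bias in the 5% against 3% comparison depends on how many enrolments are steered and how far exposure differs. The documents give neither.

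**The case against.** A reader might infer three stronger things. The documents do not support them.

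- **That each village has its own series and one team sees all of it.** Section 6.3 says trial site, undefined. The protocol elsewhere refers to site investigators, to internal monitoring by sites and to sites publishing their own data, which suggests a larger unit. No section says who opens the envelopes. So 88 is an assumption. A longer series is no harder to learn, but several teams each seeing part of one would learn less.
- **That the block size is fixed, so concealment fails.** Fixed size is inferred from a singular noun. The choice is left to the statistician, varying sizes are not excluded, and another equally reliable procedure is permitted. Even with a known block of 4, two thirds of allocations are not determined. With learning counted over 88 envelopes, 75–88% are not predictable at 95% confidence.
- **That the primary comparison is biased beyond repair.** Staff would have to track the sequence and act on it, and nothing suggests they would. SAP Table 1 shows baseline balance and Table 5 compares forest nights by arm. Those tables can reveal measured imbalance. The SAP's mixed models address repeat episodes, so neither they nor the tables can be relied on to correct unmeasured selection.

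It is also fair that the change may come late: enrolment was planned for September 2019 to July 2020, and SAP section 3.6 refers to interim analysis in the past tense.

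These objections limit the claim. They leave the core: against prediction from past allocations, the one safeguard the protocol states is a withheld size, and in an open-label trial that can be learned.

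**Conclusion.** Adequate concealment is not assured by the procedure as written. If the block size is fixed and the same staff see most of a series, about a fifth to a third of allocations are certain once the size is known, for blocks of 4 to 8. Over an assumed 88 envelopes with learning counted, the figure is about 12–25% for blocks of 4 to 10. Selective enrolment by expected forest exposure could then bias the primary comparison, by an amount that cannot be derived from the documents. If sizes already vary, the remaining defect is that the protocol does not say so. The change is worth making because it is cheap and removes most of the certain allocations.

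**What to change.** In section 6.3, replace the sentence on block size with text to this effect: *allocation uses permuted blocks of randomly varying size within each site; the sizes and their order are not disclosed to site staff and are held in a restricted document.* Define the site that holds an envelope series. Apply this to every series not yet issued. If all have been issued, report the block scheme used and who held and opened the envelopes.

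The cost is one re-run of the list generator and a few sentences; the sample size is unchanged. The downside is a slightly larger possible imbalance between arms at the end of a site's series. With a 4/6 or 4/6/8 mix, certain allocations fall to about 2–6%, while best-guess accuracy stays near 68–69%. The protocol should not describe this as a complete remedy.
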